# 2.3 Sample Size

Assuming a reduction from baseline in breast density of 6% on active and 2% on placebo, with a common standard deviation of 8%, a sample size of 272 subjects will achieve a power of 90%, using a two sample, two-sided t-test at a significance level of < 0.01. Considering an attrition rate of 15%, 330 subjects are planned for enrollment in this study.

# 3. STATISTICAL METHODS

#### 3.1 General

All data will be analyzed using the Statistical Analysis System (SAS®; Version 9.2 or higher).

Safety and efficacy data will be summarized and presented by treatment group and time point in summary tables. Continuous variables will be presented by descriptive statistics: n, mean, standard deviation, median, minimum, and maximum. Categorical variables will be tabulated by frequency count and percentage.

When the actual treatment received by a subject is different from the randomized treatment assigned, the subject will be analyzed per the randomized treatment for the efficacy parameters (using the ITT population); while the subject will be analyzed per actual treatment that was taken for the safety parameters (using the safety population).

Where appropriate, all statistical tests will be two-sided hypothesis tests performed at the 5% level of significance for main effects and all confidence intervals will be two-sided 95% confidence intervals.

#### 3.2 Subject Disposition, Demographics, Baseline Characters and Study Drug Compliance

- Subject disposition will be summarized for all enrolled subjects.
- Demographics and baseline characters will be summarized on ITT population using descriptive statistics.
- General medical history, breast cancer history, menstrual history and concomitant medications data will be summarized on ITT population.
- Study drug compliance will be summarized by visit using descriptive statistics. The compliance (%) is defined as the percentage of drug administrated as planned dose, which will be calculated as below

 $\frac{\text{Weight (g)of dispensed canisters} - \text{Weight (g)of returned canisters}}{3.52g \times \text{ number of days of treatment period}} \times 100\%$ 

The expected weight of daily dose is based on BHR "Rule of Thumb" guidance below.

- 4 squirts is an 8 mg/day dose.
- Each squirt is supposed to be 1 mL.
- 1 mL of gel = 0.88 g (based on the density of the gel: 0.88g/mL).
- 4 squirts (mL)×0.88 g/mL = 3.52 g expected in a normal 8mg/day dose day.

Sections 4.1.1 and 4.2.1 list the planned summary tables and data listings for blinded phase. Sections 5.1.1 and 5.2.2 list the planned summary tables and data listings for open-label phase.

Drug compliance will be calculated only for the subjects who returned all canisters dispensed. Drug compliance will be set as missing for the subjects who didn't return all canisters dispensed.

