#### 5.3 Dose Reduction

If a subject experiences toxicity that may make her want to stop taking study drug, the dose of study drug will be reduced by 50%, to 2 mg (1 pump actuation) to each breast. The reduced dose will be maintained for the duration of the study.

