#### 6.5 Dosage and Administration

The first dose of treatment will be applied under the supervision of the PI or designee at the clinical site. Thereafter, subjects will self-apply either BHR-700 gel or placebo as 2 fixed unit doses daily to each breast. The gel should not be applied to any other parts of the body, including the neck, abdomen, or genitals. It is advised to apply study drug in the morning after showering and to wash hands with soap and water after application. Night-time application is acceptable, but caution should be taken to limit transfer to other individuals. Application should occur approximately at the same time daily. A subject study drug administration guideline is provided in Appendix 2.

When a canister is used for the first time, it must be primed. To prime the canister, remove the cap from the canister and push the pump all the way down until gel is dispensed. Complete the priming process by pushing the pump all the way down an additional three (3) times. Do not use any gel that comes out while priming. Discard the gel by washing it down the sink to avoid accidental exposure to others. It is only necessary to prime the pump before the first dose is dispensed. Repeat priming each time a new canister is opened. After priming, the canister is ready to use. One complete press of the pump will deliver approximately the same amount of gel each time. The Investigator (or designee) will demonstrate this to each subject and will prime the study drug canister(s) prior to dispensing to the subject.

If a subject misses a dose by more than 12 hours, that dose should be noted as missed and the subject should wait for the next scheduled time before applying investigational product.

If a subject experiences toxicity that may make her want to stop taking study drug, the dose of study drug will be reduced by 50%, to 2 mg (1 pump actuation) to each breast. The reduced dose will be maintained for the duration of the study.

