#### 8.0 ASSESSMENTS OF SAFETY

#### 8.1 Adverse Event Collection and Reporting

#### • Adverse Event Collection

AEs will be captured for the duration of the study. The reporting period begins with the first dose of study drug (Study Day 1) and ends at Week 52 and Week 104. The Adverse Events eCRF must be completed for all reported AEs and SAEs.

For this study, an AE is defined as: "Any untoward medical occurrence in a patient or clinical investigation subject administered a pharmaceutical product and which does not necessarily have a causal relationship with this treatment." This includes any newly occurring event or previous condition that has increased in severity or frequency since the administration of study drug.

AEs may also be reported spontaneously at any time. Details of any adverse or unexpected events, signs, and symptoms will be collected including details of onset, resolution, frequency, severity (as defined below), seriousness, relationship to the drug, effect on the study drug, treatments administered, and outcome. Any AE will be followed, whenever possible, until it returns to the baseline condition or becomes stable with no further change expected.

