#### 1.2 Design

This is a multi-center, randomized, double-blind, placebo-controlled study in women identified as having dense breast tissue upon screening mammography.

Subjects who give informed consent will have screening evaluations, including hormone measures of FSH, Estradiol and Estrone to determine menopausal state. Those subjects meeting entry criteria, will be stratified, based on their hormone levels, into pre/peri and post menopause groups and randomized within those groups 2:1 to receive either 8 mg/day (4 mg/breast) BHR-700 gel or placebo for up to 52 weeks. At the Principal Investigator's (PI) discretion, subjects may be allowed to reduce the dose to 4 mg/day (2 mg/breast) in cases of intolerance.

Subjects will apply the gel to both breasts once per day. The first dose will be applied under the supervision of the PI/designee. Subsequent doses will be self-administered daily by the subject until she has completed 52 weeks of study drug administration. Study drug compliance will be checked at each study visit. Subjects will be asked to capture daily gel administration in a diary and drug canisters will be weighed on release to the subject and on return. The canister weight will be recorded in grams. If the study drug is discontinued or interrupted, the reason(s) will be recorded. During treatment period, subjects will be evaluated at Day 1 and every 13 weeks (±2 weeks) thereafter.

A planned sample size of 330 women, identified as having dense breast tissue upon screening mammography, will be randomized to receive either BHR-700 gel or placebo (at 2:1 ratio). Considering an attrition rate of approximately 15%, it is expected to have 272 evaluable women (4-OHT: 181 & Placebo: 91) who will have both baseline and 52 week measurements of percent mammographic density (MD) of the breast.

Subjects who complete the double-blind phase of the study will be offered entry into an open-label follow-up period for an additional 52 weeks.

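### The compliance formula divides by a full-dose 3.52 g/day for every woman, so full adherence to the permitted half dose scores about 50%, the same as missing half of the full doses

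*SAP*

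**What the plan says.** SAP 3.2 introduces the measure with these words: "The compliance (%) is defined as the percentage of drug administrated as planned dose". The formula is the weight of canisters dispensed minus the weight returned, divided by 3.52 g times the days of treatment. The constant comes from 4 actuations of 1 mL at 0.88 g/mL, described as "3.52 g expected in a normal 8mg/day dose day". SAP 3.7 repeats the fixed 3.52 g for each visit interval, with the day count set to the difference between visit dates plus 1.

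The same documents provide for a second dose level. SAP 1.2 says that "subjects may be allowed to reduce the dose to 4 mg/day (2 mg/breast) in cases of intolerance". Protocol 5.3, repeated in 6.5, says that "the dose of study drug will be reduced by 50%, to 2 mg (1 pump actuation) to each breast", and then: "The reduced dose will be maintained for the duration of the study".

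Neither formula has a term, an alternative denominator or a flag for days on the reduced dose. The percentage is summarised by visit in Table TSD01a (blinded phase) and listed in LSD01a and LSD01b (blinded and open-label phases).

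**The concern.** A compliance percentage is read as how far a woman did what she was asked to do. With a denominator fixed at the full dose, a woman who has been moved to half the actuations and applies every one of them looks like a woman who skips half her treatment. Because the reduction is lasting, the low score recurs at every later visit.

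What is at stake is the background to the results that remain. After early termination, SAP 3.8 limits the report to a brief one centred on safety and PK/PD. A reader looking at adverse events or plasma concentrations will want to know whether low gel use reflects a permitted reduction or missed doses. The percentage as defined cannot answer that. No title in the SAP's output lists (sections 4 and 5) names dose reduction, exposure or dose intensity.

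**Working it through.** **Inputs**
- Gel weight per actuation: 0.88 g (SAP 3.2).
- Full dose: 4 actuations a day (SAP 3.2).
- Reduced dose: 1 actuation per breast, so 2 a day (protocol 5.3 and 6.5).
- Visit interval: 13 weeks = 91 days, within ±2 weeks (SAP 1.2).
- By-visit day count: difference between visit dates + 1 (SAP 3.7).

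**The plan's own constant.** 4 × 0.88 = 3.52 g/day, which matches SAP 3.2.

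**Expected weight on the reduced dose.** 2 × 0.88 = 1.76 g/day.

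**Score = 100 × grams used / (3.52 × days), for a 91-day interval (denominator 3.52 × 91 = 320.32 g)**
- Full dose, fully adherent: 320.32 / 320.32 = 100%.
- Reduced dose throughout, fully adherent: 1.76 × 91 = 160.16; 160.16 / 320.32 = 50.0%.
- Full dose, half the doses missed: 3.52 × 45.5 = 160.16; 160.16 / 320.32 = 50.0%.

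The last two women use the same weight of gel, so the formula cannot separate them.

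**With the extra day in SAP 3.7 (92 days, denominator 323.84 g).** Both score 160.16 / 323.84 = 49.5%.

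**Reduction part-way.** If the change falls at mid-interval, the adherent woman scores (100 + 50)/2 = 75% for that interval. If it falls at Week 13, the blinded-phase value, which SAP 3.7 takes as the average of the visit values, is (100 + 50 + 50 + 50)/4 = 62.5% with no dose missed. With the extra day it is 62.5 × 91/92 = 61.8%.

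**After the repair.** With the denominator set to the weight prescribed each day, the adherent reduced-dose woman scores 160.16 / 160.16 = 100%. The full-dose woman who misses half stays at 160.16 / 320.32 = 50%. The two are now told apart.

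**The extra day on its own.** Four 91-day intervals give 4 × 92 = 368 days in the denominators. From Day 1 to the Week 52 visit, both included, there are 4 × 91 + 1 = 365 days. The surplus of 3 is the Week 13, 26 and 39 visit days, each counted twice. For a fully adherent full-dose woman with 91 days of use in the interval, the loss is 1 − 91/92 = 1.1 points. In a 63-day interval (Week 15 to Week 24, the shortest the windows allow between two scheduled visits) it is 1 − 63/64 = 1.6 points.

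**The case against.** **The planned dose may mean the randomised 8 mg/day.** That is the only dose in the objectives, and on this reading a score of 50% is a correct statement of gel received. The reading is fair, but the quantity is then dose intensity under the name of compliance, and the two women still share one score. The objection changes the label needed; it does not remove the fault.

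**Nothing of weight depends on the number.** This stands. SAP 2.1, 3.5 and 3.7 tie the per-protocol set to no compliance cut-off, SAP 3.3.2 plans no efficacy analysis, and plasma 4-OHT is measured directly. A reader might infer that the formula distorts the per-protocol set or the efficacy results; the documents give no route by which it could.

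**Other records may identify the reductions.** Also fair. A daily diary is kept, and protocol 8.1 collects for each adverse event its "relationship to the drug, effect on the study drug, treatments administered, and outcome". The listing templates are not visible here. So the stronger inference, that the trial's records cannot show who was reduced, is not supported. The claim is confined to the percentage.

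**No reduction rate is given.** This stands as well. A reader might infer that group compliance, or that of the active arm in particular, is materially understated. Each woman wholly on the reduced dose loses 50 points, so a visit mean would fall by 1, 2.5 or 5 points if 2%, 5% or 10% of women were reduced and all were fully adherent. Those proportions are assumptions, and nothing in the documents supports one over another or a difference between arms.

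**Priming gel might be counted as use.** One could infer that priming inflates the scores. Protocol 6.5 says "Repeat priming each time a new canister is opened", but also that the investigator or designee "will prime the study drug canister(s) prior to dispensing to the subject", and protocol 6.8 has canisters weighed on release. The natural reading is that priming comes before weighing, so no inflation is claimed. The order could simply be stated.

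**The right place for the extra day depends on when gel is applied.** Protocol 6.5 advises morning use but accepts night-time use, so visit-day gel may come from the old or the new supply. The double count of shared visit days remains, but no single interval is the correct home for the extra day in every woman.

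**Conclusion.** The point holds at the level of the individual percentage. A fully adherent woman on the permitted reduced dose scores about 50% (49.5% with the extra day) in any interval spent wholly on that dose, identical to a full-dose woman who misses half her doses. This follows from the SAP's own 0.88 g and 3.52 g and the two actuations in protocol 5.3. It assumes only that each actuation delivers its nominal 1 mL and that the weights capture applied gel.

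Severity is low. The measure is descriptive, and the number of women affected is not given, so no group-level size can be claimed. The double-counted visit days are a secondary matter of about 1 point. SAP 3.7's unweighted averaging of visit values is not raised as a fault, since the documents give no basis for sizing its effect. No view is taken on the dose-reduction rule itself.

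**What to change.** In SAP 3.2 and 3.7, define compliance (%) as 100 × grams used / sum over days of (actuations prescribed that day × 0.88 g). Report grams used relative to the 8 mg/day weight as a second measure labelled dose intensity, so that lower exposure stays visible.

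Take the reduction date from dosing records or from the adverse-event field on study-drug effect. Where no date is recorded, flag the reduced-dose intervals and summarise them separately. The rule that sets compliance to missing when canisters are not all returned can stay.

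Two small additions: use one day count in both sections that counts each treatment day once across consecutive intervals, and state whether the release weight is taken after priming.

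The cost is a few lines of SAP text and minor programming. The downside is reliance on a recorded reduction date, which no section of either document guarantees.

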#### 3.3 Analysis of Study Endpoints

#### 3.3.1 Safety Analysis

The safety analysis will be conducted on safety population. The safety population includes all subjects who received at least one dose of study drug.

#### Adverse Events

- All adverse events (AE) will be summarized with MedDRA primary system organ class (SOC) and preferred term.
- Summary tables of severe AEs, SAEs and study drug related AEs will also be provided.
- Listings of all AE, serious adverse events (SAE), and severe AEs will be provided.

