1.3 Study Synopsis

Study Title:	A Randomized, Double-Blind, Placebo-Controlled Trial of
~~~~~~	4-Hydroxytamoxifen Gel for Reducing Breast Tissue Density in
	Women with BI-RADS Breast Density Categories C or D
Development Phase:	Phase 3
Investigational Product	BHR-700, 4-Hydroxytamoxifen (afimoxifene) gel
(IP):	
Active Pharmaceutical	4-Hydroxytamoxifen (4-OHT)
Ingredient (API):	
Study Centers:	Multicenter study conducted in approximately 25 centers
Study Duration:	Up to 110 weeks per subject: 2 weeks screening, 52 weeks blinded
	treatment period with an optional 52 weeks open-label extension.
Study Objective	
Primary:	To determine the efficacy of 8 mg/day (4 mg/breast) of BHR-700 gel
	compared to placebo for reducing breast tissue density in women
	identified as having dense breast tissue upon analysis of screening
	mammography using the Food and Drug Administration
	(FDA)-cleared Cumulus 2D software.
Study Endpoints	
Primary:	The percentage reduction of mammographic breast tissue density on
•	a follow-up mammogram compared to the baseline mammogram
	after 52 weeks of treatment.
Secondary:	Incidence and severity of adverse events (AEs) with special attention
J = 1 = 1 = 1	given to uterine abnormalities, cardiovascular events,
	thromboembolic events, and incidence of vasomotor symptoms ("hot
	flush").
	Change in serum concentration of sex hormone binding globulin (SHBG).
	Change in serum concentration of: cholesterol, triglycerides, high-density lipoprotein (HDL), and low-density lipoprotein (LDL).
	Change in serum concentration of Protein C-activity, Protein S- activity, Antithrombin 111 antigen, and Activated Protein C resistance (APCR).
	Change in serum concentration of select bone biomarkers CTx and BSAP.
	Plasma concentrations of the E and Z isomers of 4-OHT.
Study Design	
Methodology:	This is a multi-center, randomized, double-blind, placebo-controlled study in women identified as having dense breast tissue upon screening mammography.
	Subjects who give informed consent will have screening evaluations, including hormone measures of FSH, Estradiol, Estrone and LH to

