	15. Women with a concurrent illness, disease or condition that, in the
	opinion of the Investigator, would limit their compliance with
	study requirements or place them at additional risk.

Test Product, Dose, and Mode of Administration:	The BHR-700 gel formulation contains 2 mg/mL 4-OH tamoxifen (0.2%) in a clear, colorless, absorptive hydro-alcoholic gel base formulated to provide continuous release of 4-OH tamoxifen. The BHR-700 gel is supplied in a non-aerosol canister with a 1 mL fixed-dose pump.
	Two (2) fixed unit doses of BHR-700 gel will be applied daily to each breast. Each actuation dispenses 1 mL of gel. A total of 8 mg/day (4 mg/breast) of 4-OHT will be administered daily, unless dose reduction by the Investigator, is deemed necessary for reasons of tolerability.
	The placebo gel is identical in appearance and consistency to the BHR-700 gel.
	Treatment compliance will be monitored by the Investigator staff who will check subject diaries and weigh the IP canister(s) when dispensed and upon return.
Duration of Treatment:	Up to 52 weeks for primary efficacy assessment with an optional and additional 52 weeks of open-label treatment of BHR-700 gel.
Criteria for Evaluation	
Efficacy Measures:	Mammograms will be centrally analyzed. The reader will be blinded as to the treatment group (BHR-700 gel or placebo) and time point of each subject. Cumulus 2D will be the primary endpoint method with Volpara 3D as a secondary endpoint method.
Safety Measures:	
 
Safety assessments will include evaluation of all AEs/serious adverse events (SAEs), with special attention given to uterine abnormalities, cardiovascular events, and thromboembolic events. Additional important safety parameters specific for this indication are: 
 
Endometrial changes
 
Breast evaluation
 
Coagulation factors
 
Bone biomarkers
 
Changes in menstrual cycle; unexpected vaginal bleeding
 
 
 

	To address these safety parameters, subjects will undergo the following assessments:
	A bilateral mammogram with both the raw and processed 2D image DICOM files needs to be performed within 3 months prior to randomization. The same (make/model/serial number) mammography machine must be used for the Week 52 mammogram, and if the subject is participating in the Open-Label phase, the Week 104 mammogram. If the mammogram is older than 3 months but less than 18 months, or it cannot be provided in the format required for

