#### **Secondary Outcome Measures:**

- Comparison of the reduction in breast density as calculated with the Volpara method and the Cumulus method.
- Laboratory parameters will be summarized in a descriptive fashion.
- Incidence and severity of AEs will be compared between BHR-700 gel and placebo.

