#### 2.2.2 Secondary Endpoints

- 1 The percentage reduction in breast density at Week 52 using two breast density measurement methods (Cumulus versus Volpara).
- 2 The percentage of women who underwent a change in BI-RADS category when comparing pre-and post-treatment measurements.
- 3 The percentage of women with a ± 10% absolute decrease in quantitative mammographic density (Cumulus) between baseline and 52 weeks,
- 4 Change in serum concentration of: cholesterol, triglycerides, high-density lipoprotein (HDL), and low-density lipoprotein (LDL).
- 5 Change in serum concentration of sex hormone binding globulin (SHBG).
- 6 Change in serum concentration of Protein C-activity, Protein S-activity, Antithrombin 111 antigen, and Activated Protein C resistance (APCR).
- 7 Change in serum concentration of select bone biomarkers CTx and BSAP.
- 8 Incidence and severity of AEs and laboratory values.
- 9 The menstrual cycle of premenopausal women.
- 10 Pharmacokinetic (PK) plasma concentration of the E and Z isomers of 4-OHT after 13, 26, 52, 78, and 104 weeks of application of 4 mL BHR-700 gel to the breasts.

The secondary endpoints are for both blind and open-label treatment phases.

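### The SAP drops the adverse-event groups named in the protocol's secondary endpoint and plans no table of women with at least one event in each group

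*SAP*

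**What the plan says.** **Protocol.** The secondary endpoints in the synopsis (section 1.3) include "Incidence and severity of adverse events (AEs) with special attention" "given to uterine abnormalities, cardiovascular events" and "thromboembolic events, and incidence of vasomotor symptoms". For vasomotor symptoms the stress is on incidence. The Safety Measures entry of the same synopsis repeats three of the four groups: "with special attention given to uterine abnormalities, cardiovascular events, and thromboembolic events". Section 9.1, Secondary Outcome Measures, states: "Incidence and severity of AEs will be compared between BHR-700 gel and placebo". Section 8.3 defines three severity grades: mild, moderate and severe.

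**SAP endpoint.** Section 2.2.2 item 8 reads "Incidence and severity of AEs and laboratory values". None of the four groups is named. Section 3.8, which records changes to the protocol's planned analysis, does not mention the omission.

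**SAP analysis.** Section 3.3.1 states: "All adverse events (AE) will be summarized with MedDRA primary system organ class (SOC) and preferred term". It then adds: "Summary tables of severe AEs, SAEs and study drug related AEs will also be provided". Sections 4.1.2 and 5.1.2 list TAE01 to TAE06 for the blinded phase (suffix a) and the open-label phase (suffix b). Section 3.1 says that summaries are by treatment group. Outside the adverse-event tables, an endometrial table (TEM01a, section 4.1.3) and listing (LEM01a, section 4.2.3) are planned for the blinded phase if data exist.

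**The concern.** When a protocol singles out groups of events in a safety endpoint, a reader expects to find, for each arm, how many women had at least one event of each kind and how severe it was. The SAP fixes the output list, and protocol 9.1 gives the SAP precedence over the protocol's statistical section where the two differ. If the list is followed exactly, those counts are not produced.

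More hangs on this than it would in a completed trial. After early termination, SAP 3.3.2 plans no efficacy analysis for the study report, and SAP 3.8 directs the report to safety and PK/PD. Protocol 2.2 bases the case for a topical product on limiting systemic adverse effects, and lists earlier topical doses only up to 4 mg/day, whereas this trial uses 8 mg/day. With fewer women and shorter exposure, related events are likely to appear as scattered single cases under different terms. A grouping fixed in advance is what allows them to be read together.

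**Working it through.** The plan states no figure to reproduce here. The check is a comparison of texts, followed by a short counting argument.

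**1. Groups in each place**

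| Place | Uterine | Cardiovascular | Thromboembolic | Vasomotor |
|---|---|---|---|---|
| Protocol 1.3, secondary endpoints | named | named | named | named (incidence) |
| Protocol 1.3, Safety Measures | named | named | named | not named |
| SAP 2.2.2 item 8 | no | no | no | no |
| SAP 3.8, changes | no | no | no | no |
| TAE01–TAE06, by title | no | no | no | no |
| TEM01a and LEM01a | endometrial only, blinded phase, if data exist | no | no | no |

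There are 6 adverse-event tables per phase, so 6 + 6 = 12. By title, none is organised by group. No section of the SAP text defines a group by a list of preferred terms or a MedDRA query.

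**2. Can the group count be derived from the planned rows?** Suppose a group consists of k preferred terms, and the table shows n1, …, nk women for them in one arm. Let W be the number of women with at least one event in the group. Then

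max(n1, …, nk) ≤ W ≤ n1 + … + nk (and W cannot exceed the arm size).

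The lower limit applies when every woman counted in the smaller rows is also in the largest row. The upper limit applies when no woman is in two rows. With illustrative counts:

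- Rows 2, 1, 1: max = 2 and sum = 2 + 1 + 1 = 4, so W lies between 2 and 4.
- Rows 3, 2, 2, 1: max = 3 and sum = 3 + 2 + 2 + 1 = 8, so W lies between 3 and 8.

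For a single term, k = 1 and W = n1. Hot flush is therefore readable by arm if it is coded to one term.

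**3. Do the organ-class rows settle it?** Only if a group coincides with one organ class. Otherwise the row mixes group events with others, or holds only part of the group. The SAP does not say which terms form a group, so no row can be matched to one.

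**4. Severity.** Of the three grades, only severe has its own table by title (TAE04a/b). SAP 3.4.1 counts an event with missing severity as severe, so that table also contains ungraded events. TAE01a/b might hold rows for mild and moderate. Its shell is not in the text available, so this can be neither confirmed nor excluded.

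**5. Listings.** LAE01a (all adverse events) with LRN01a (randomisation) would let someone count each woman once per group by arm. The choice of terms would then be made with the events and the allocation in view.

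**The case against.** The best reply is that the SAP covers more than its first bullet on adverse events suggests, and that the protocol promises less. The special-attention wording stands only in the synopsis. Protocol 9.1 and the numbered secondary objectives name no groups, and SAP item 8 is close to the 9.1 wording. Nowhere does the protocol promise a pooled count or a term list.

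That is accurate and keeps the point modest, but it does not remove it. The synopsis is where the protocol sets out its endpoints, and the groups are part of this one.

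A reader might also infer several stronger things that the documents do not support:

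- **That events are counted only by organ class and preferred term.** Severe, serious and drug-related events have their own tables, by arm.
- **That group incidence cannot be obtained from the report at all.** The listings permit it, though only post hoc.
- **That mild and moderate events are never shown by arm.** The missing shell of TAE01a leaves this open.
- **That all four groups are risks of oral tamoxifen named in the rationale.** Protocol 2.2 names endometrial cancer, thromboembolic events, vasomotor symptoms, arthralgia and cataracts. Cardiovascular events are not in that list.
- **That an excess of some particular size would be hidden.** The documents give no event rates for these groups and no achieved enrolment, so no such size can be stated.

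The SAP's emphasis on descriptive statistics (section 1.3) is no answer, because the missing table is itself descriptive.

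**Conclusion.** The point holds as a gap in pre-specified safety reporting. The SAP omits the event groups that the protocol attaches to its adverse-event endpoint, does not record the omission as a change, defines none of the groups, and lists no table of women with at least one event per group. The planned preferred-term rows give limits for that count and not its value, except where a group is a single term.

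The size is best stated as what is absent: group-level counts for uterine, cardiovascular and thromboembolic events in both phases, with partial cover for endometrial findings in the blinded phase. The row counts used above are illustrative and are not trial data. The conclusion needs no assumed rate. It rests on one condition, that a group contains more than one preferred term, and on the SAP text and table titles, since the shells were not available. If the TAE01 shell turned out to contain severity rows, the remark on mild and moderate would fall. The absence of group definitions in the SAP text would remain.

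This is an inexpensive improvement worth making. It is not a flaw that invalidates the safety report.

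**What to change.** 1. Restore the synopsis wording, with its four groups, in SAP 2.2.2 item 8.
2. Fix the preferred-term list for each group before database lock and unblinding. SAP 2.1 already uses that timing for identifying major protocol deviations.
3. Add one descriptive table per phase, counting each woman once per group at her maximum severity (mild, moderate, severe). Show the blinded phase by treatment group. Show the open-label phase overall, or by original randomised arm, because all women then receive the gel.

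A general re-layout of TAE02 by maximum severity for all events is not needed for this purpose.

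The cost is a change of SAP wording, a one-off term list drawn up while blinded, and one extra table per phase. No new data are collected.
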